3.1 Screening and Eligibility

All patients seen in our Adult Comprehensive Sickle Cell Center will be screened for eligibility. Currently, there are greater than 450 patients actively seen and an average of 60 patients seen per week. The same inclusion/exclusion criteria will be used for both arms of the study.

Inclusion Criteria

[figure not shown]
- documented HgbSS, SC or HgbS-beta⁰ thalassemia,
- age ≥ 18 years old and ≤ 80 , seen in outpatient clinic ≥ 2 times in past year, and
- seen for an acute care visit (hospitalization, emergency department, or day hospital visit) for pain > 2 times in the past year.

Impact of Daily Prophylaxis Dose Anticoagulation with a Factor Xa Inhibitor (Apixaban) in Patients with Sickle Cell Disease

Exclusion Criteria

- Hospitalization or day hospital visit for pain crisis within the past 2 weeks
- Patients with ≥ 10 acute care visits within the past year will be excluded
- Creatinine > 3.0 mg/dL
- creatinine ≥ 1.5 mg/dL AND **weight** ≤ 60 kg
- chronic use of antiplatelet or anticoagulation medication
- Patients with known vasculopathy or Moya-Moya
- platelet count $< 100 \times 10^9/L$
- AST or ALT > 3 times normal
- chronic red blood cell transfusions (scheduled transfusions)
- packed red blood cell transfusion within the past 2 months
- Use of CYP3A4 and P-gp inhibitor medications

4.0 Specific Aim 1. Evaluate the impact of daily prophylactic dose anticoagulation (oral direct factor Xa inhibitor) on daily pain scores in outpatients with SCD.

4.1 Study Procedures Aim 1

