principal investigator. Pain scores during hospitalization and for the subsequent 1 week will be recorded and used for secondary analysis of daily pain scores during crisis.

Patients who during the course of the study have laboratory findings which reveal creatinine ≥ 1.5 mg/dL AND weight ≤ 60 kg; platelets $< 100 \times 10^9/L$; or develop AST or ALT > 3 times normal, will have study drug stopped and will be terminated from the study.

Patients on hydroxyurea will be included in the study and sub-analysis will be performed to control for potential differences. All patients despite treatment with hydroxyurea will need to meet inclusion criteria of having clinically significant pain which requires > 2 acute care visits.

4.2 Data and Statistical Analysis Aim 1

We power the study to test whether there is a significantly larger reduction in pain after administration of a daily prophylactic anticoagulation dose as compared to administration of a placebo. A total of 60 patients will be randomly assigned to each drug arm. The primary endpoint is the mean pain score per patient over each of four time periods. The design has two sources of variation: the variation between the patients receiving the same drug and the variation due to the interaction of time by the patients within drug arm. It is of interest to test whether the change in the pain score over the four time periods differs between the prophylactic anticoagulation dose arm and the placebo arm. From the literature the standard deviation of the mean pain score per patient is 1.5. Assume the true mean pain scores over the four time periods for the placebo and prophylactic anticoagulation dose arms are 3.9, 3.9, 3.9, 3.9 and 3.9, 3.12, 3.12, 3.12, respectively. Then, a total of 60 patients randomized equally to each drug arm will detect the difference in the change between the two arms in the mean pain scores over time, as specified by the preceding mean pain scores, with a power of at least 0.836 for a one-sided 0.05 test. Anticipating that 20% (10 patients) may have incomplete data (less than 75% of daily pain scores recorded or missing more than one dose of study drug per week), may be lost to follow up, or may drop out; we have also found a power of at least 78.4% for 50 patients.

We expect two positive effects from prophylactic doses of apixaban on the patient reported outcomes:

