- PROs assessing fatigue, physical function, and pain impact will improve in patients administered daily prophylactic dose apixaban compared to placebo.*
- We believe that there will be a significant correlation between PROs and pain scores.*

Statistical Analysis

The primary outcome of interest is to test the effect on the mean daily pain score due to the arm by time interaction. Secondary outcome will include comparison of daily pain scores while hospitalized between treatment arms and the number of hospitalizations during each treatment period.

Impact of Daily Prophylaxis Dose Anticoagulation with a Factor Xa Inhibitor (Apixaban) in Patients with Sickle Cell Disease

[figure not shown]
All analyses will be performed using SAS version 9 or greater (SAS Institute Inc., Cary, NC). Data will be analyzed using descriptive statistics including mean and standard deviation. Comparisons are to be performed using SAS's PROC GLM with a model that accounts for all fixed and random effects in the design.

5.0 Specific Aim 2: Determine the effect of prophylactic dose anticoagulation on markers of thrombin generation during outpatient steady state as well as inpatient VOC.

As described in section 3.0, we will perform a double blind, parallel group, placebo controlled feasibility study with an enrollment target of 60 patients (30 per arm).

5.1 Study Procedures Aim 2

As described earlier (Figure 1), patients begin a 1 month observation following randomization. Patients will have blood drawn on enrollment and when they return in 1 month (+/- 5 days) to begin study drug. Subsequent blood draws performed at 2 month intervals while on study drug. Blood draws will occur between 2 and 4 hours from previous dose taken and ± 5 days regardless of hospitalization. Patients will be called monthly between in person visits to assess for AE/SAE and to reinforce the importance of medication compliance. Graded incentives may be given monthly to encourage patients to continue on study and return for follow up blood draws.

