5.2 Data and Statistical Analysis

Sample Size

The same design used in Aim 1 applies to Aim 2. We analyze the change in thrombin generation from enrollment to 2 months following initiation of study drug. We hypothesize that the anticoagulation drug will

Impact of Daily Prophylaxis Dose Anticoagulation with a Factor Xa Inhibitor (Apixaban) in Patients with Sickle Cell Disease

cause a decrease in thrombin generation from baseline to two months. From the literature the standard deviation of the D-dimer measure per patient is 500. With a total of 60 patients randomized equally to each drug sequence, and conservatively assuming no correlation between D-dimer values from baseline to 2 months on the same patient, we achieve a power of 0.863 to detect a mean D-dimer difference in the change from baseline to 2 months between the placebo and the daily prophylactic anticoagulation dose groups of 250 mg/l $\{= [(1000-750) - (1000-1000)] \text{ mg/l}\}$ for a one-sided 0.05 test.

No studies to date have evaluated the influence of anticoagulants on thrombin generation as measured by CAT, therefore sample size and expected differences are calculated based on available studies examining D-dimer.

Statistical Analysis

For our primary outcome, we will compare mean changes in thrombin generation (D-dimer, TAT and phases of CAT) for patients treated with prophylactic dose anticoagulation and placebo. Secondary outcomes will include correlation of hypercoagulable and inflammatory markers to clinical outcomes (such as pain, hospitalization, and number of acute care visits).

In addition, we expect that 50% of the patients to be hospitalized and continue their medication (placebo or drug) as assigned at randomization. For these patients, thrombin generation D-dimer measures will be collected at admission, 3 days and 5 days. Therefore, as a secondary aim, for these hospitalized patients we will analyze the difference between the placebo and drug groups in the change over time in the mean D-dimer values.

Planned Analysis of Primary Endpoint

Following the enrollment of the 60 patients, and completion of the 7 month study period for each patient, all data will be subsequently analysed with the assistance of the Duke Translational Medical Institute. [name] is our lead statistician who will continue to provide statistical support and analysis through this study.

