Primary analysis of daily pain scores will be performed for patients on treatment with Apixaban and compared to patients on placebo, to determine if treatment decreases daily pain scores. In addition, we will compare changes in thrombin generation from enrollment to 2 months for patients treated with Apixaban versus placebo.

Secondary analysis will be performed to evaluate differences when patients are hospitalized and on study drug versus placebo, as well as healthcare utilization for patients treated with Apixaban.

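### The between-arm comparison of hospitalizations, and of healthcare utilization if it is compared, names no prior-year count as a baseline covariate; adding one offers a modest gain in precision

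*Combined protocol and SAP*

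**What the plan says.** - **Outcomes.** Section 4.2 (Statistical Analysis) makes "the number of hospitalizations during each treatment period" a secondary outcome. The Planned Analysis of Primary Endpoint in section 5.2 adds "healthcare utilization for patients treated with Apixaban", without a measure, comparator or model. Elsewhere in section 5.2, acute care visits appear only among the clinical outcomes to be correlated with laboratory markers ("such as pain, hospitalization, and number of acute care visits").
- **Model.** Section 4.2 specifies "PROC GLM with a model that accounts for all fixed and random effects in the design". No baseline covariate is named. Section 3.0 describes computerized randomization and mentions no stratification.
- **Adjustment.** The only adjustment mentioned is for hydroxyurea, in section 4.1: "sub-analysis will be performed to control for potential differences".
- **Eligibility.** Section 3.1 includes patients "seen for an acute care visit (hospitalization, emergency department, or day hospital visit) for pain > 2 times in the past year" and also states "Patients with ≥ 10 acute care visits within the past year will be excluded".

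**The concern.** Because there is an upper limit as well as a lower one, screening staff cannot stop counting at the third visit. A prior-year count must be made for all 60 patients, and it is close to a baseline value of the utilization outcome. The plan uses baseline values for its other outcomes: pain is analysed as change over four periods, and D-dimer as change from enrollment. For hospitalizations and healthcare use it names none.

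With 30 patients per arm, a chance difference in prior use enters an unadjusted arm comparison directly, and predictable differences between patients stay in the error term. What is at stake is the precision of secondary comparisons. Section 2.0 presents avoiding admissions as a purpose of the trial, so that precision has some value.

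**Working it through.** The plan gives no rate, SD or power for hospitalizations or acute care use, so there is no figure of its own to reproduce.

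**Inputs from the documents:** 60 patients, 30 per arm and 6 months on drug (section 3.0); prior-year limits of more than 2 and fewer than 10 (section 3.1); 50% of patients expected to be hospitalized (section 5.2, covering both arms, with no period given).

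**Assumptions:** the distribution of prior counts, the link between prior and on-study rates, overdispersion, and each patient's probability that a visit is an admission.

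**1. Range.** More than 2 and fewer than 10 gives 3 to 9, so observed counts can differ by 9/3 = 3. Expected rates differ less. For gamma-distributed rates the ratio is (shape + 9)/(shape + 3): 10/4 = 2.5 at shape 1 and 11/5 = 2.2 at shape 2.

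**2. Closed form, with the total prior-year count k as covariate.** Let μ be the expected on-study count given k, and θ the overdispersion.

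- R² = Var(μ) / [Var(μ) + E(μ) + θE(μ²)]
- Net variance ratio = (1 − R²)(1 + 1/56)

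Take k uniform on 3 to 9: mean 6, variance 4, squared coefficient of variation 4/36 = 0.111.

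- *Acute care visits*, μ = k/2, θ = 0: R² = 1/(1 + 3) = 0.25; net ratio 0.763.
- Same, θ = 0.5: R² = 1/(1 + 3 + 5) = 0.111; net ratio 0.905.
- Half proportionality, θ = 1: R² = 0.25/(0.25 + 3 + 9.25) = 0.02; net ratio 0.997.
- *Hospitalizations*, mean 0.722 (set so that 50% have at least one), full proportionality, θ = 0: Var(μ) = 0.722² × 0.111 = 0.058; R² = 0.058/(0.058 + 0.722) = 0.074; net ratio 0.942.
- Half proportionality, mean 0.700, θ = 0: R² = 0.019; net ratio 0.998.

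With right-skewed k included, the net ratio runs from about 0.76 to 1.00 for acute care visits and 0.93 to 1.00 for hospitalizations. At a mean below about 1, Poisson noise dominates, so total visits predict admissions poorly.

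**3. Simulation, with each outcome's own baseline.** Annual visit rates were gamma (means 3–4, shapes 1–2), patients were kept if the prior-year count was 3–9, and follow-up was half a year. The arm effect was estimated with and without the covariate.

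| Outcome | Covariate | Admission tendency | Fall in variance |
|---|---|---|---|
| Acute care visits | log prior-year visits | not used | 8–12% |
| Hospitalizations | log(prior-year admissions + 0.5) | same for all, 0.33 | none, up to 1% loss |
| Hospitalizations | same | beta(2,4) | 4–6% |
| Hospitalizations | same | beta(1,2) | 15–17% |
| Hospitalizations | log prior-year visits | same for all | 1–5% |

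The hospitalization rows for prior-year admissions come from a linear model. A quasi-Poisson fit put the two beta settings together at about 9–18%. Across a further set of gamma settings, the acute care figure spanned 3–13%. Type I error was about 4–6% with or without the covariate.

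In sample-size terms, 8–12% is like 60/0.92 = 65 to 60/0.88 = 68 patients. In power terms (one-sided 0.05), acute care visits at an assumed rate ratio of 0.6 went from 0.67 to 0.72 in one setting. Hospitalizations at an assumed rate ratio of 0.5 went from 0.49 to 0.55 in the most favourable setting.

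**4. Where the covariate can act.** If counts per period were tested for arm-by-time with patient effects in the model, a value that is constant within a patient is absorbed by those effects. In a balanced 60 × 4 example the residual sum of squares was identical with and without it. The gain exists only for the between-arm main effect.

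**The case against.** The case against acting is substantial, and most of it limits the point without removing it.

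- **Unclear comparison.** The more dependable gain belongs to acute care visits, whose comparison between arms is only loosely implied by the healthcare utilization sentence. This stands; that part applies only if such a comparison is made.
- **Data not necessarily on file.** A reader might infer that both counts are already extracted. Section 3.1 pools admissions, emergency and day hospital visits into one threshold, so the prior-year hospitalization count need not exist as a field. The lower limit counts visits for pain and the upper limit all acute care visits, so there is no single ready-made variable. This stands.
- **Threefold risk.** A reader might infer that patients enter with event rates up to three times apart. That describes observed counts; the expected ratio under the gamma-Poisson assumption is 2.2 to 2.5.
- **Assumption-driven size.** No document gives the spread in admission tendency. If all patients share one tendency, the gain for hospitalizations is nil. This stands.
- **No refusal to adjust.** The plan is silent on covariates, and the hydroxyurea sub-analysis shows some intent to adjust. Silence still leaves the choice until after the data are seen.
- **Status of the outcome.** This is a feasibility study, the outcome is secondary, and no power is claimed for it. This stands and sets the weight of the point.

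**Conclusion.** The point holds as a modest, optional gain in precision. The plan names no baseline covariate for these comparisons, although its own eligibility rules require prior-year visits to be counted for everyone. Under the gamma-Poisson assumptions, adjustment cuts variance by about 8–12% for acute care visits. For hospitalizations the cut is roughly 0–17%, with its size set by an unknown spread in admission tendency.

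A reader might go further and infer that the unadjusted comparison is biased or invalid, or that a large amount of precision is being lost. The documents do not support either. Randomization protects the unadjusted comparison, simulated type I error is the same both ways, and for hospitalizations the gain may be zero.

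**What to change.** In section 4.2 and the Planned Analysis in section 5.2, prespecify for the between-arm main effect:

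- **Hospitalizations on treatment:** adjust for the prior-year hospitalization count, for example as log(count + 0.5).
- **Acute care visits on treatment, if compared between arms:** adjust for the log prior-year acute care visit count, under one stated definition (all acute care visits, or pain visits only).
- **Data capture:** record both counts as numbers at screening, not only an eligibility yes or no, and split out admissions while the visits are being counted.

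Name the covariates before unblinding, so that the choice cannot appear data-driven. The cost is a sentence in each section, two data fields, a little extra record abstraction, and one degree of freedom per model, which is about 1% of variance at worst.

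### Section 4.2 counts 20% of 60 patients as 10 instead of 12, and does not say whether incomplete patients stay in the primary pain analysis

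*Combined protocol and SAP*

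**What the plan says.** All in the combined protocol and SAP.

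- **Sample size (section 4.2).** 60 patients in total give power of at least 0.836 for a one-sided 0.05 test of the difference between arms in change over time. The text continues: "Anticipating that 20% (10 patients) may have incomplete data", then "we have also found a power of at least 78.4% for 50 patients".
- **What counts as incomplete (section 4.2).** "less than 75% of daily pain scores recorded or missing more than one dose of study drug per week", pooled with loss to follow-up and dropout.
- **Endpoint (section 4.2).** "The primary endpoint is the mean pain score per patient over each of four time periods".
- **Analysis (section 4.2, Statistical Analysis).** The primary test is the arm-by-time interaction. The only method named is "PROC GLM with a model that accounts for all fixed and random effects in the design".
- **Hospital days (section 4.1).** "Pain scores during hospitalization and for the subsequent 1 week will be recorded and used for secondary analysis of daily pain scores during crisis". Section 4.2 lists in-hospital pain as a secondary outcome. In section 5.2, "we expect that 50% of the patients to be hospitalized".
- **Who is analysed (section 5.2, Planned Analysis of Primary Endpoint).** "Primary analysis of daily pain scores will be performed for patients on treatment with Apixaban and compared to patients on placebo". A preceding sentence says that all data are analysed once every patient has finished; it concerns timing.

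No section names an analysis set for the pain endpoint, a rule for missing scores or a sensitivity analysis.

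**The concern.** The percentage and the count in one sentence disagree, and the reduced power is attached to the smaller loss. A reader who relies on the 20% takes from the plan a power that belongs to a loss of 16.7%.

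The diary and missed-dose criteria describe what patients do after randomisation. Giving a power for those who remain implies that the others leave the analysis, but this is never stated as a rule. Because the endpoint is a mean per period, a patient with a thin diary or some missed doses may still supply all four values. Two analysts following the text could therefore analyse 60 patients or about 48. The two analyses differ in power. If incompleteness relates to pain differently by arm, they also differ in the estimate. The choice should be fixed before unblinding.

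**Working it through.** **Inputs from the plan.** 60 patients, 30 per arm (sections 3.0 and 5.0; the section 4.2 sentence is read as a total). SD 1.5. Means 3.9 in all four periods on placebo, and 3.9 then 3.12 three times on drug, so the effect is 0.78. One-sided 0.05. Powers 0.836 at 60 and 0.784 at 50. No within-patient correlation is given.

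**1. The count.** 0.20 × 60 = 12, leaving 48. 10/60 = 16.7%, leaving 50. Ten is 20% of 50, not of 60.

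**2. The plan's own power.** It cannot be reproduced without a correlation ρ. Assume that period 1 precedes drug, that correlations are equal, and that the test contrasts the mean of periods 2–4 with period 1. Then Var(change) = 1.5² × (1 − ρ) × (1 + 1/3) = 3(1 − ρ), and SE = √[3(1 − ρ) × 2/30]. Power 0.836 needs 0.78/SE = 0.978 + 1.645 = 2.623, so SE = 0.297 and ρ ≈ 0.56. The figure for 50 gives about 0.57 in the same way.

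**3. Power at 48.** A single-degree-of-freedom test can be rescaled without ρ, because the standardised effect grows with √N.

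- From 0.836 at 60: Φ(2.623 × √(48/60) − 1.645) = Φ(0.701) = 0.758.
- From 0.784 at 50: Φ((0.786 + 1.645) × √(48/50) − 1.645) = Φ(0.737) = 0.769.
- Cross-check, 0.836 taken to 50: Φ(2.623 × √(50/60) − 1.645) = 0.773, about one point under the stated 0.784.

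So power at 48 is 76–77%, about 1.5 points below the power at 50 on either base. If 0.836 came instead from a 3-df F test at 0.05 (ρ ≈ 0.75), the figures would be 0.754 at 50 and 0.734 at 48. That fits the stated 0.784 less well, and such a test is not one-sided.

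**4. Keeping or removing the incomplete patients** (ρ = 0.57 assumed, t-based, 20% affected, all four means present):

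- effect 0.78 in everyone, all kept: power 0.837;
- 20% removed at random (24 per arm): 0.758;
- all kept, but the 20% gain nothing, so the average effect is 0.8 × 0.78 = 0.624: 0.677.

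Keeping and removing break even when the average effect is 0.695, which is 89% of 0.78. For ρ = 0.4 and 0.7, power is 0.719 and 0.933 at 30 per arm, and 0.633 and 0.877 at 24 per arm. Power alone does not decide the analysis set.

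**5. GLM or mixed model under true dropout** (simulation, 10,000 runs, ρ = 0.57, SD 1.5, 30 per arm). Where dropout depends on pain, its log-odds rise by 1 or 2 per SD of the last recorded pain; ranges cover both. Negative bias favours the drug. The Monte Carlo SE of the bias is 0.003.

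| Scenario | Row-per-period GLM | Likelihood model, unstructured |
|---|---|---|
| 20% random, effect 0.78: power | 0.802 | 0.804 |
| Same link in both arms, no effect: bias | −0.001 to 0.001 | −0.001 |
| Same, one-sided error | 5.1–5.2% | 5.0–5.1% |
| Same link, effect 0.78: bias | −0.009 to −0.016 | −0.004 to −0.005 |
| Link in placebo only, 20%, no effect: bias | −0.070 to −0.109 | −0.007 to −0.008 |
| Same, one-sided error | 7.6–9.4% | 5.1–5.2% |
| Link in placebo only, 10%, no effect: bias | −0.030 to −0.051 | 0.001 |
| Same, one-sided error | 5.8–6.6% | 4.8–5.0% |

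The largest bias is 0.109/0.78 = 14% of the planned effect. With ρ from 0.4 to 0.7 (6,000 runs), the 10% placebo-only case gives GLM bias of −0.026 to −0.079 and error of 6.0–7.7%.

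**The case against.** The count is an editorial slip: the 78.4% is openly tied to 50 patients, and two patients fewer cost about 1.5 points. An evaluable set is arguably implied already. On the method, GLM does little harm in the ordinary cases. Appreciable bias needs pain-driven dropout in one arm only, for which a double-blind trial's documents offer no basis. All of this stands, and it limits the size of the point. It does not make 10 equal to 20% of 60, nor does it turn an implication in a power paragraph into an analysis rule.

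Stronger readings that a reader might infer, and that the documents do not support:

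- **PROC GLM will delete every patient with a missing period.** The REPEATED form would. But section 4.2 names two sources of variation, between patients and time by patients within arm, and asks for random effects. That describes a split-plot, row-per-period layout, which keeps available periods.
- **The primary result will be biased.** The 20% pools partial diaries, missed doses and dropout, and no rates by arm are given. The table shows what could happen, not what is expected.
- **Section 5.2 plans an as-treated analysis.** Its wording most naturally just labels the arms.
- **Hospital days corrupt the primary endpoint.** Sections 4.1 and 4.2 assign those scores to secondary analysis, so secondary-only is a reasonable reading. Some doubt remains: section 5.1 expressly keeps inpatient blood draws out of the primary analysis, and no matching sentence exists for pain. The effect cannot be sized, because 50% hospitalised gives no number of days.

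**Conclusion.** The count or the percentage in section 4.2 is wrong as written. If 20% is meant, 48 patients remain and power is about 76–77%, assuming a one-sided single-degree-of-freedom test. If 10 patients are meant, the loss is about 17% and the stated 78.4% can stay. The error is small, plain and free to correct.

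Naming the analysis set and using a likelihood mixed model is a cheap improvement, not the repair of a demonstrated bias. The reason to analyse all randomised patients is that the exclusion criteria arise after randomisation; the power figures point both ways. The reason for the mixed model is protection if dropout follows recorded pain differently by arm. Under random dropout it gives essentially no power over row-per-period GLM. The figures in steps 4 and 5 rest on a correlation of 0.57, which is back-solved and not a plan input.

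**What to change.** In section 4.2:

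1. Correct the loss either to 12 patients (48 remaining) with power restated to about 76–77%, or to 17% (50 remaining) with 78.4% kept.
2. State that the primary analysis includes all randomised patients in their assigned arm, with all available period means regardless of adherence. Fit arm, period and arm-by-period by a likelihood mixed model for repeated measures (for example PROC MIXED with REML), and name the covariance structure. Keep the stated interaction as the test.
3. Make the 75%-diary and adherence criteria a per-protocol sensitivity analysis.

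Minor: reconcile the missed-dose wording (section 4.1 allows up to two a week, while section 4.2 counts more than one as incomplete), since the per-protocol set depends on it. State whether hospital-day scores enter the primary period means. Settle when randomisation occurs, because it defines the set: section 3.0 places it after the observation month, while sections 4.1, 5.1 and 6.1 place it before.

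The cost is a few sentences and a different SAS procedure, with no new patients, visits or data. The downside is an estimate that includes non-adherence. It may be smaller, and power would be lower if non-adherent patients gain little.
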